4.2. Secondary endpoints

Regarding Secondary Objective 1:

The feasibility of forefoot surgery using a specific block of the two distal branches of the tibial nerve, combined with a block of the superficial and deep peroneal nerves and the saphenous nerve, will be assessed by the fact that no additional anesthetic technique is required to perform the surgery.

Regarding Secondary Objective 2:

Ultrasound identification of the plantar arteries and plantar nerves below the midfoot axis will be assessed using a Numerical Scale for Identification of the Medial and Lateral Plantar Nerves (ENR-Plantar Nerves): a numerical scale ranging from 0 (no visualization) to 100 (extremely easy visualization).

Regarding Secondary Objective 3:

Patient satisfaction and comfort during the ALR procedure will be assessed using three numerical scales:

- Patient satisfaction is assessed using an Analog Numeric Scale (ANS-Satisfaction) ranging from 0 (very dissatisfied) to 100 (very satisfied).
- Pain assessment during regional anesthesia uses a Numerical Analog Scale (NAS-R) ranging from 0 (no pain) to 100 (extremely painful).
- Pain assessment during peripheral venous access (PVA) uses an ANS (ANS-PVA) ranging from 0 (no pain) to 100 (extremely painful). It will serve as a reference for the ANS-ALR.

Regarding secondary objective 4:

Any sensory-motor complications will be assessed using a questionnaire (Appendix 1) during a phone call with the patient on Day 15±4 and at 1 month during the follow-up visit with the surgeon.

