2. SCIENTIFIC RATIONALE AND GENERAL DESCRIPTION OF THE RESEARCH

2.1. Study Context

Surgery for forefoot conditions (such as hallux valgus, ingrown toenails, foot wounds, metatarsal fractures, Morton's neuroma, etc.) is a painful procedure typically performed on an outpatient basis. Effective pain management is crucial, and regional anesthesia (RA) is currently the gold standard technique (1–3). Blockade of the sciatic nerve and/or its branches is the most appropriate analgesic technique. The innervation of the foot depends exclusively on this nerve.

The sciatic nerve block has long been performed in the popliteal fossa or on the thigh (4). However, this technique causes motor block of the tibialis anterior and triceps surae muscles. The former causes a steppage gait, while the latter results in an inability to lock the knee. Early resumption of walking therefore requires the use of a knee brace and canes (5). This technique, long used for hospitalized patients, is therefore poorly suited for outpatient forefoot surgery.

Trunk blocks of the distal branches of the sciatic nerve (tibial and fibular) at the ankle have been considered to maintain ankle joint mobility, thereby facilitating early discharge home while ensuring effective pain relief (6,7) (Figures 1 and 2). The tibial nerve block at the ankle allows for anesthesia of the various branches of this nerve: the medial plantar branch (medial plantar nerve), the lateral plantar branch (lateral plantar nerve), and the calcaneal branches. This block is combined with blocks of the deep and superficial peroneal nerves. This technique is an effective alternative for forefoot surgery. Nevertheless, the loss of cutaneous sensation and deep (or proprioceptive) sensation in the heel theoretically carries a risk of falling. Indeed, the loss of proprioception results in the abolition of the medial plantar reflex (flexion of the toes upon percussion of the plantar arch), as well as an absence of muscle contraction of the triceps surae. Early discharge is therefore feasible, either without weight-bearing using crutches, or with cautious weight-bearing and crutches, for patients who have been informed of the risk of falling.

[figure not shown]

Figure 1: Anatomy of the sciatic nerve

[figure not shown]

Figure 2: Branches of the sciatic nerve at the ankle

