5.2.2. In the operating room

a) Anesthesia

Patient preparation:

Upon arrival in the operating room, the patient will be positioned under the conditions necessary and recommended for performing the ALR:

- Placement of a peripheral intravenous line (PIVC),
- Low-flow nasal oxygen therapy,
- Strict aseptic technique,
- Monitoring: ECG, NIBP, and SpO₂.

Pain assessment at the time of PIVC placement will be obtained from the patient using the ENA-PIVC scale.

Patients will not receive premedication or deep sedation during the LAR procedure. However, in cases of significant discomfort, light sedation may be offered, as is standard for all LAR techniques.

The ALR will be performed systematically under ultrasound guidance.

Performing ultrasound-guided ALR:

The ALR will be performed 45 minutes before surgery, and its effectiveness will be verified before transfer to the operating room.

The patient will be placed in the supine position for the various procedures. All procedures will be performed using an ultrasound machine (Logic E – General Electric). The transducer (L8-18 linear transducer – General Electric) will be positioned to provide an axial view of the nerves. 22-gauge, 50-mm needles (BBraun – Stimuplex Ultra 360) designed for regional anesthesia will also be used. The needle will be inserted either in the ultrasound plane (IP) or out of the ultrasound plane (OOP). Prior to each procedure, skin disinfection will be performed using an alcoholic iodine solution. 5 to 7 mL of 0.375% ropivacaine, a local anesthetic (LA), will be injected at the point of contact with each nerve.

All patients will receive a block of the superficial and deep fibular nerves, a saphenous nerve block, as well as the lateral and medial plantar nerves below the MC axis.

Pain assessment during ALR will be collected from the patient using the ENA-ALR.

- *Performing the deep peroneal nerve block*

The ultrasound probe will be positioned on the anterior edge of the ankle. The dorsal artery of the foot will be initially identified, and the deep peroneal nerve will be located in contact with it. The local anesthetic will be injected in contact with the artery or the nerve.

- *Performing the superficial peroneal nerve block*

The superficial peroneal nerve is specifically blocked at the lateral border of the leg directly over the fibula, beneath the superficial fascia.

[figure not shown]

Performing the deep peroneal nerve block

E Albrecht, [name], H Cadas, V Moret.

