Based on the Practical Manual of Ultrasound-Guided Regional Anesthesia

Elsevier - Masson, Paris, 2014

Performing a superficial peroneal nerve block

E Albrecht, [name], H Cadas, V Moret.

adapted from Practical Manual of Ultrasound-Guided Regional Anesthesia
Published by Elsevier-Masson, Paris, 2014

- *Performing a saphenous nerve block*

An infiltration of the medial edge of the foot will be performed systematically.

- *Performing the specific lateral and medial plantar nerve block*

The line connecting the center of the medial malleolus and the medial calcaneal tuberosity (MC axis) will be marked prior to performing the block.

The ultrasound probe will be positioned at the medial edge of the foot below this line. The two plantar branches of the tibial nerve will be identified, as well as the tibial plantar arteries. The local anesthetic will be injected in contact with the neurovascular bundle.

The anesthesiologist will assess the identification of the plantar arteries and nerves below the MC axis using the ENR-Plantar Nerves protocol.

Position of the ultrasound probe for performing a block of the distal branches of the tibial nerve at the ankle

Sensory tests:

The cold test and touch test will be performed every 10 minutes for 40 minutes following the injection of local anesthetics into the specific territories of each nerve.

The anesthesiologist will record the sensory score for each branch of the tibial nerve.

At 40 minutes, a detailed sensory map of the sole of the foot will be created.

Recording of potential complications:

The occurrence of any paresthesia, indicative of nerve damage, will be noted. The anesthesiologist will ask the patient during the procedure about any sensations of discomfort: tingling, numbness, or other prickling sensations.

If regional anesthesia fails—defined as the inability to perform the surgery—the anesthesiologist will use the standard anesthesia technique: a tibial nerve block at the ankle above the mid-calf line.

b) Surgery

The surgical procedure will be performed according to standard practice.

Any intraoperative complications will also be noted.

The patient's satisfaction score will be assessed at the end of surgery.

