12.5. Identification of all data to be collected in the observation log

Demographic data:

- Age
- Gender
- Height
- Weight

Preoperative data:

- Date of surgery
- Type of surgery
- Intraoperative events: Use of standard anesthesia technique
- Volume of local anesthetic per nerve
- Time of regional anesthesia, time of surgery, time of surgery completion
- Sensory scores (from the cold test and touch test) recorded every 10 minutes during the 40 minutes following local anesthetic injection,
- Mapping of the plantar arch based on sensory scores,

- ENR-Plantar nerves
- ENA-VVP
- ENA-ALR
- ENA-Satisfaction
- Intraoperative complications

Postoperative data:

- Possible complications (see Appendix 1: questionnaire)

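### Feasibility counts any added anesthetic as failure of a five-nerve block, but the only rescue prescribed, and the only one with its own data item, is a heel-numbing tibial block

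*Combined protocol and SAP*

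**What the plan says.** Section 4.2 defines surgical feasibility for the plantar block "combined with a block of the superficial and deep peroneal nerves and the saphenous nerve". With the medial and lateral plantar nerves that makes five nerves, and section 5.2.2 gives all five blocks to every patient. The endpoint "will be assessed by the fact that no additional anesthetic technique is required to perform the surgery". Section 8.1 analyzes it as a proportion with a 95% confidence interval.

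Section 5.2.2 defines failure of the regional anesthesia as not being able to operate, without reference to which block failed. In that event "the anesthesiologist will use the standard anesthesia technique: a tibial nerve block at the ankle above the mid-calf line" (the line is read here as the MC axis used elsewhere in the section). No other rescue is named.

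On what that block does, section 2.1 states: "The tibial nerve block at the ankle allows for anesthesia of the various branches of this nerve". It lists the medial plantar, lateral plantar and calcaneal branches, and says that the fibular (peroneal) nerves are blocked in addition. The same section warns that "the loss of cutaneous sensation and deep (or proprioceptive) sensation in the heel theoretically carries a risk of falling".

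On data, section 12.5 has one rescue item: "Intraoperative events: Use of standard anesthesia technique". It also lists the volume of local anesthetic for each nerve, the sensory scores and intraoperative complications. Section 5.2.2 adds: "The anesthesiologist will record the sensory score for each branch of the tibial nerve".

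**The concern.** The endpoint is wider than both the rescue rule and the data item that serve it. Two things follow.

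- **Care.** If a fibular or saphenous block fails and section 5.2.2 is followed to the letter, the patient receives a block that does not reach the painful territory. It also removes heel sensation in a foot where the plantar block may have worked as intended. That sensation is the benefit under study.
- **Measurement.** If the anesthesiologist does the sensible thing and infiltrates, or goes to general anesthesia, the patient is a failure under section 4.2, but section 12.5 has no item that asks about it. A failure that is not recorded is counted as a success.

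Section 8.2 says the pilot is meant to show quickly whether the method is worth a comparative study. The feasibility proportion is one of the two results with a planned confidence interval, so an avoidable upward error in it matters even though no success threshold is set.

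**Working it through.** **1. The plan's own figures.** Section 8.2 tabulates 95% intervals for a proportion with N = 50. The formula p ± 1.96 × √(p(1 − p)/50) gives widths of 0.1663 at p = 0.10 (stated 0.166) and 0.2772 at p = 0.50 (stated 0.278). All nine widths agree within 0.001 and all limits agree to three decimals. Nothing below changes that table.

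**2. Does the rescue reach the failed territory?** Nerves are from sections 4.2 and 5.2.2, and the reach of the tibial block is from section 2.1.

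| Nerve blocked | Within tibial territory? |
|---|---|
| Medial plantar | Yes |
| Lateral plantar | Yes |
| Superficial fibular | No, blocked separately |
| Deep fibular | No, blocked separately |
| Saphenous | No, not a listed tibial branch; infiltrated separately |

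Three of the five nerves lie outside the prescribed rescue. For the two plantar nerves the rule works, at the cost of heel sensation.

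**3. Is each supplement captured?**

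| Supplement | Failure under 4.2? | Where 12.5 would show it |
|---|---|---|
| Tibial block | Yes | Dedicated item |
| Repeat fibular or saphenous block | Yes | No dedicated item; the volume for that nerve should show extra drug |
| Local infiltration | Yes | No dedicated item |
| General anesthesia | Yes | No dedicated item |
| Intraoperative sedation | Not classified | No dedicated item |

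**4. Can the cause of a failure be traced?** Largely. Section 4.1 scores the medial and lateral plantar nerves at 40 minutes and requires 0 on both for success. A patient with 0 on both who still needs a supplement points to a companion block; one with a score above 0 points to the plantar block. Which companion nerve failed is not clearly recorded.

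**5. Illustration only.** The documents give no block failure rates. Assume that each of the three companion blocks fails independently with probability p and that every failure needs a supplement. The share of patients with at least one such failure is 1 − (1 − p)³.

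| Assumed p | 1 − (1 − p)³ | Expected of 50 |
|---|---|---|
| 0% | 0 | 0 |
| 1% | 1 − 0.99³ = 3.0% | 1.5 |
| 2% | 1 − 0.98³ = 5.9% | 2.9 |
| 5% | 1 − 0.95³ = 14.3% | 7.1 |

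The share is lower if failures cluster in the same patients or if the operation spares the failed territory.

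The bias runs from zero (all supplements recorded) to the whole share (none recorded). In the second case, with no other failures, the report would read 50/50 = 100% (exact 95% CI 92.9 to 100%). The truth would be 47/50 = 94% (83.5 to 98.7%) at p = 2%, or 43/50 = 86% (73.3 to 94.2%) at p = 5%. These are extremes, not expected values.

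**The case against.** The strongest reply is that the tibial block is naturally read as the fallback for the experimental part only. The companion blocks are routine, nothing forbids topping them up, and no anesthesiologist would give a tibial block to a patient whose sole is documented as numb. Section 5.2.2 also says of the regional anesthesia that "its effectiveness will be verified before transfer to the operating room", and section 5.7 lets the investigator suspend participation in the patient's interest. Section 2.1 calls the fall risk theoretical and allows discharge with crutches.

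This makes the harmful sequence unlikely, but the text stays as it is: the trigger is any inability to operate, and one response is named. The sensible departure from it is also the one with no data item of its own.

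On data, the objection is stronger. Section 10.2 requires all protocol information in the eCRF, and a supplement that decides a secondary endpoint is such information. Volume per nerve should reveal a repeat block. Section 5.2.2 also speaks of testing in the territory of each nerve, so companion nerves may be tested, although the sentence on recording names the tibial branches. These points stand. They narrow the gap to supplements such as infiltration and general anesthesia, and they make wholesale loss of such cases improbable.

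A reader might infer that the study cannot tell plantar failure from companion-block failure. The documents do not support that, because the 40-minute plantar scores largely make the distinction. Nor do they support counting sedation as failure: section 4.2 does not class it as an additional technique, and section 5.2.2 allows light sedation for discomfort during the blocks as ordinary practice.

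**Conclusion.** The point holds as a mismatch between an endpoint that covers five nerves and any supplement, and a rescue rule and data item that cover one supplement suited to two of those nerves. Followed literally after a fibular or saphenous failure, the rule gives an ineffective block and numbs the heel; this follows from sections 2.1 and 5.2.2 and needs no assumed rate.

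The effect on the feasibility proportion is a possible overstatement that the documents do not allow to be quantified. It is zero if every supplement is recorded. The 94% and 86% examples rest on assumed failure rates, independence, a supplement for every failure and no recording at all, so they should not be read as a forecast.

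It would also go too far to infer that the main result is compromised. The primary endpoint is scored at 40 minutes and surgery is planned 45 minutes after the blocks, so a rescue given after the test leaves it untouched. The sample size is unaffected. Endpoint 1 can be scored as written, provided the supplements are known. This is a point to consider before the eCRF is fixed, not a defect in the design.

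**What to change.** **Section 5.2.2.** Limit the tibial rescue to failure in a plantar territory. For a fibular or saphenous failure, prescribe a repeat block or infiltration of that territory, which keeps heel sensation. Use general anesthesia if these fail.

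**Section 12.5.** Replace the rescue item with: *Any additional anesthetic technique required for surgery: Y/N; type; territory*. Score endpoint 1 from it, with every Y a failure. Record intraoperative sedation in its own field rather than counting it automatically as failure.

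**Section 8.1.** Cross-tabulate endpoint 1 failures against the 40-minute plantar scores, which are already collected.

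The cost is a short rescue rule, a slightly longer eCRF entry and one descriptive table, with no extra patients or visits. The reported feasibility figure may be less favorable, because supplements that might have gone unrecorded will be counted.

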5. RESEARCH METHODOLOGY

5.1. Study Type

Single-center, prospective, non-randomized, open-label study.

This is a pilot study seeking to demonstrate the feasibility of a specific block of the two distal branches of the tibial nerve for forefoot surgery, while preserving heel sensation.

5.2. Research Procedure

The research protocol includes the following steps:

5.2.1. Inclusion

The patient will be informed of the protocol by an investigator during the anesthesia consultation. Clear and accurate information will be provided to the patient both verbally and in writing (see information sheet). The physician will verify the inclusion and exclusion criteria.

If the patient agrees to participate in the study after a reflection period they deem sufficient, a consent form will be provided to them. This form must then be dated and signed by the investigator and the patient.

5.2.2. In the operating room

a) Anesthesia

Patient preparation:

Upon arrival in the operating room, the patient will be positioned under the conditions necessary and recommended for performing the ALR:

- Placement of a peripheral intravenous line (PIVC),
- Low-flow nasal oxygen therapy,
- Strict aseptic technique,
- Monitoring: ECG, NIBP, and SpO₂.

Pain assessment at the time of PIVC placement will be obtained from the patient using the ENA-PIVC scale.

Patients will not receive premedication or deep sedation during the LAR procedure. However, in cases of significant discomfort, light sedation may be offered, as is standard for all LAR techniques.

The ALR will be performed systematically under ultrasound guidance.

Performing ultrasound-guided ALR:

The ALR will be performed 45 minutes before surgery, and its effectiveness will be verified before transfer to the operating room.

The patient will be placed in the supine position for the various procedures. All procedures will be performed using an ultrasound machine (Logic E – General Electric). The transducer (L8-18 linear transducer – General Electric) will be positioned to provide an axial view of the nerves. 22-gauge, 50-mm needles (BBraun – Stimuplex Ultra 360) designed for regional anesthesia will also be used. The needle will be inserted either in the ultrasound plane (IP) or out of the ultrasound plane (OOP). Prior to each procedure, skin disinfection will be performed using an alcoholic iodine solution. 5 to 7 mL of 0.375% ropivacaine, a local anesthetic (LA), will be injected at the point of contact with each nerve.

All patients will receive a block of the superficial and deep fibular nerves, a saphenous nerve block, as well as the lateral and medial plantar nerves below the MC axis.

Pain assessment during ALR will be collected from the patient using the ENA-ALR.

- *Performing the deep peroneal nerve block*

The ultrasound probe will be positioned on the anterior edge of the ankle. The dorsal artery of the foot will be initially identified, and the deep peroneal nerve will be located in contact with it. The local anesthetic will be injected in contact with the artery or the nerve.

- *Performing the superficial peroneal nerve block*

The superficial peroneal nerve is specifically blocked at the lateral border of the leg directly over the fibula, beneath the superficial fascia.

[figure not shown]

Performing the deep peroneal nerve block

E Albrecht, [name], H Cadas, V Moret.

Based on the Practical Manual of Ultrasound-Guided Regional Anesthesia

Elsevier - Masson, Paris, 2014

Performing a superficial peroneal nerve block

E Albrecht, [name], H Cadas, V Moret.

adapted from Practical Manual of Ultrasound-Guided Regional Anesthesia
Published by Elsevier-Masson, Paris, 2014

- *Performing a saphenous nerve block*

An infiltration of the medial edge of the foot will be performed systematically.

- *Performing the specific lateral and medial plantar nerve block*

The line connecting the center of the medial malleolus and the medial calcaneal tuberosity (MC axis) will be marked prior to performing the block.

The ultrasound probe will be positioned at the medial edge of the foot below this line. The two plantar branches of the tibial nerve will be identified, as well as the tibial plantar arteries. The local anesthetic will be injected in contact with the neurovascular bundle.

The anesthesiologist will assess the identification of the plantar arteries and nerves below the MC axis using the ENR-Plantar Nerves protocol.

Position of the ultrasound probe for performing a block of the distal branches of the tibial nerve at the ankle

Sensory tests:

The cold test and touch test will be performed every 10 minutes for 40 minutes following the injection of local anesthetics into the specific territories of each nerve.

The anesthesiologist will record the sensory score for each branch of the tibial nerve.

At 40 minutes, a detailed sensory map of the sole of the foot will be created.

Recording of potential complications:

The occurrence of any paresthesia, indicative of nerve damage, will be noted. The anesthesiologist will ask the patient during the procedure about any sensations of discomfort: tingling, numbness, or other prickling sensations.

If regional anesthesia fails—defined as the inability to perform the surgery—the anesthesiologist will use the standard anesthesia technique: a tibial nerve block at the ankle above the mid-calf line.

b) Surgery

The surgical procedure will be performed according to standard practice.

Any intraoperative complications will also be noted.

The patient's satisfaction score will be assessed at the end of surgery.

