4. EVALUATION CRITERIA

4.1. Primary Endpoint

The primary endpoint is the success of the procedure, defined as the successful selective block of the plantar branches of the tibial nerve, anesthesia of the distal foot while preserving heel sensation, and the absence of paresthesia.

The success of the selective block of the plantar branches of the tibial nerve will be assessed using a sensation score for each branch of the tibial nerve.

A cold test and a touch test will be performed every 10 minutes for 40 minutes following the injection of local anesthetics.

The touch test will be performed using a 2-point sensitivity measurement device (Touch-Test).

The cold test will be performed using a cold roller (Rullo “Oerlikon” nizell.ch).

The tests will be performed on specific areas of the tibial nerve:

- calcaneal branches: calcaneus;
- medial plantar nerve: medial part of the arch of the foot;
- lateral plantar nerve: lateral part of the arch of the foot.

A contralateral assessment will be performed to accurately determine the sensory score.

Score/Contralateral side: 2: normal sensation, 1: decreased sensation, 0: total loss of sensation.

The success of the selective block will be confirmed if the following results are obtained at 40 minutes:

- calcaneal branches = 2
- medial plantar nerve = 0
- lateral plantar nerve = 0

At 40 minutes, a precise mapping of the plantar arch will be performed to determine the exact extent of sensory loss (Figure 4).

The degree of paresthesia during the procedure will be assessed by asking the patient about any sensations of discomfort: tingling, numbness, or other prickling sensations.

[figure not shown]

Figure 4: Example of a plantar arch mapping

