5.6. Description of measures taken to reduce or avoid bias

To avoid selection bias, this study will be offered to all eligible patients seen in the anesthesia clinic. For eligible patients who are not included, the reason for exclusion will be noted.

The evaluation criterion is sufficiently objective to avoid any assessment bias.

5.7. Description of the rules for permanently or temporarily terminating a person's participation in the research, procedures for monitoring these individuals, and procedures for replacing these subjects, if necessary

Any subject included in the study may decide to withdraw their consent to participate in the study at any time and for any reason, without having to provide explanations or justifications and without this affecting the care they are receiving or will receive. The investigator must indicate in the patient's eCRF the date and, if applicable, the reason for the termination of participation in the research. Withdrawal of consent prohibits the use of medical data obtained after the withdrawal of consent. Data already collected regarding the subject may be used.

The investigator may temporarily or permanently suspend a subject's participation in the research for any reason that impacts their safety or that is in the patient's best interest. Data already collected regarding the subject may be used in the analysis of the study results.

A subject's withdrawal from the study will not alter their usual care.

A patient who withdraws prematurely from the study will be replaced, and a study withdrawal form will be completed, including the reason for withdrawal (Consort flow diagram).

Once the protocol-specified sample size is reached, the investigator must halt recruitment for the study. However, patients who have already signed a consent form may still be included in the study.

5.8. Identification of all data collected directly in the study's eCRF and for which no other source documents exist

Sensory scores, assessment of plantar nerve recognition, patient satisfaction and comfort scores, as well as data obtained during the telephone call on Day 15±4 by a healthcare professional, are recorded directly in the eCRF.

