10. QUALITY CONTROL AND ASSURANCE

10.1. Quality Control

The sponsor appoints a Clinical Research Associate (CRA) to conduct monitoring visits, who will ensure that:

- the rights, safety, and protection of the individuals participating in the research are upheld,
- the critical elements necessary for the analysis of the primary and secondary objectives are present,
- the reported data are accurate, complete, and consistent with the source documents,
- the research is conducted in accordance with the protocol, Good Clinical Practice (GCP), applicable laws and regulations, and in accordance with the Standard Operating Procedures established by the Research and Innovation Team at CMC Ambroise Paré (RICAP), the study sponsor.

The investigator and members of his team agree to make themselves available during visits conducted by the ARC.

During these visits, the following items will be reviewed:

- Written informed consent;
- Compliance with the research protocol and the technical procedures defined therein;

- Quality of the data collected in the observation log: accuracy, missing data, consistency of the data with the "source" documents (medical records, appointment logs, original laboratory results, etc.).

10.2. eCRF

All information required by the protocol will be recorded in an electronic case report form (eCRF), with data hosted on a central, secure server. Data will be collected as it is obtained by the investigator and/or personnel designated by the investigator.

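### The plan names no assessor independent of the treating anesthesiologist and requires neither screening of the feet nor a test order, so the section 5.6 statement on assessment bias is not supported and the success rate may be overestimated

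*Combined protocol and SAP*

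**What the plan says.** Section 5.1 describes the design: "Single-center, prospective, non-randomized, open-label study". Section 8.1 confirms that there is no comparison group and that the primary result is one proportion with a 95% confidence interval.

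Section 4.1 scores each tibial branch 2 (normal), 1 (decreased) or 0 (lost) relative to the other foot. At 40 minutes, success needs a calcaneal score of 2 and medial and lateral plantar scores of 0. The endpoint also covers "anesthesia of the distal foot while preserving heel sensation, and the absence of paresthesia".

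Section 5.2.2 gives the testing in the passive voice: "The cold test and touch test will be performed every 10 minutes for 40 minutes following the injection of local anesthetics". Recording is assigned to a role: "The anesthesiologist will record the sensory score for each branch of the tibial nerve". The same role rates the ultrasound view ("The anesthesiologist will assess the identification of the plantar arteries and nerves below the MC axis using the ENR-Plantar Nerves protocol") and elicits the paresthesia component ("The anesthesiologist will ask the patient during the procedure about any sensations of discomfort: tingling, numbness, or other prickling sensations"). No other assessor appears.

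On measurement bias, section 5.6 says only: "The evaluation criterion is sufficiently objective to avoid any assessment bias". Section 5.8 lists the sensory scores among the data entered directly in the eCRF with no other source document.

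**The concern.** A graded sensation score depends on what the patient reports and on how the person recording it resolves a doubtful answer. Here the recorder belongs to the treating role and knows which pattern counts as success. The patient has been told the study's objectives, and the primary objective in section 3.1 includes keeping sensation in the heel. Expectation can therefore act on both sides. It can act at each threshold: heel 2 rather than 1, plantar 0 rather than 1.

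With no comparison group, a tendency to score generously does not cancel; it goes straight into the reported proportion. The interval reflects sampling error only. Monitoring cannot recover the truth, because section 10.1 checks data against source documents and these scores have none outside the eCRF. Section 8.2 says the result is to show the value of the method and whether a comparative study should follow, so an inflated rate could mislead that decision.

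**Working it through.** **1. Does the text support section 5.6?**

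| Question | What the documents give |
|---|---|
| Is treatment masked? | No, open-label (5.1) |
| Who records the score? | The anesthesiologist (5.2.2) |
| Who applies the tests? | Not stated |
| Is an assessor independent of the operator named? | No |
| Are the feet screened from the patient? | Not stated |
| In what order are the sites tested? | Not stated; 4.1 lists sites only |
| Is a device reading tied to 0, 1 or 2? | No; two devices are named without cut-offs (4.1) |
| Do patients know the aim? | They must be told the objectives (11.2) |

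Fixed sites, named devices, the contralateral reference and the 40-minute time point standardise the test. None blinds the scorer or the patient.

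**2. The plan's own figures.** The table in section 8.2 uses p ± 1.96 × √(p(1 − p)/50). At p = 0.10 this gives 0.017 to 0.183, width 0.166, as stated. At p = 0.50 it gives 0.361 to 0.639, as stated; the computed width is 0.277 against 0.278, a rounding difference. All nine rows agree on both limits. The table is sound as a statement of sampling error; it has no term for scoring error.

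**3. Illustration of size.** Let s be the true success rate and f the share of true failures read as success, with no true success misread. Then

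observed rate = s + f(1 − s), and shift = f(1 − s).

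The documents give neither s nor f; both are assumptions.

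| s | f | Observed | Shift (points) | 95% half-width at the observed rate, n = 50 (points) |
|---|---|---|---|---|
| 50% | 10% | 55% | 5 | 13.8 |
| 50% | 20% | 60% | 10 | 13.6 |
| 70% | 10% | 73% | 3 | 12.3 |
| 70% | 20% | 76% | 6 | 11.8 |
| 90% | 10% | 91% | 1 | 7.9 |
| 90% | 20% | 92% | 2 | 7.5 |

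In patients, a true 70% means 15 failures in 50. Misreading 10 to 20% of them means 1.5 to 3 patients.

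**4. Effect on the interval, same assumptions.** Coverage of the true rate, summed over Binomial(50, observed rate), for f = 10% and 20%:

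- s = 50%: Wald 86.7% and 66.4%; Clopper-Pearson 92.1% and 76.3%.
- s = 70%: Wald 89.5% and 79.2%; Clopper-Pearson 94.7% and 87.9%.

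With f = 0 the Wald coverage is 93.5% at both rates.

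**5. Sensitivity to the one-way assumption.** If a share g of true successes is misread as failure, the observed rate is s(1 − g) + f(1 − s). At s = 70%, f = 10%, g = 5%: 0.70 × 0.95 + 0.10 × 0.30 = 0.665 + 0.030 = 0.695. The net bias is then −0.5 points. The bias is zero when g = f(1 − s)/s, here 0.03/0.70 = 4.3%.

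**The case against.** The strongest reply is that much of the alarm would rest on things the documents do not say. A reader might infer that the person who places the block also scores it. Section 5.2.2 uses one role name throughout but does not say it is the same individual, and section 10.2 allows others to collect data ("Data will be collected as it is obtained by the investigator and/or personnel designated by the investigator"). A reader might also infer that the foot is in the patient's view, that sites are tested in a known order, or that the operator prompts the rating. The documents are silent on all three, and the site list in section 4.1 is not a sequence. These readings should not be stated as facts.

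Second, the test is standardised, with serial readings and a sensory map. A falsely generous plantar 0 also meets a later check: surgery follows, and the need for another anesthetic technique is a secondary endpoint (section 4.2).

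Third, the size is assumed and runs one way. Success needs three exact scores and no paresthesia, so undirected error could produce mainly false failures. Step 5 shows how little of it cancels the shift.

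Fourth, this is an exploratory pilot without a success threshold, where unblinded scoring is often simply disclosed.

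The first and third replies stand as limits on the claim. The second stands in part: standardisation is not blinding, and the heel score has no comparable later check. The fourth bears on severity. It does not rescue section 5.6, which denies the limitation instead of disclosing it. Silence on screening and order does not show they are absent in practice, but it does mean the plan does not require them.

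**Conclusion.** The point holds in a limited form. The plan requires no separation of operator and scorer, no screening and no test order, and the endpoint is a graded judgement in an open-label, single-arm study. The claim in section 5.6 does not follow from the design. Overestimation is the plausible direction, because the scorer knows the success pattern and patients are told the objectives, but it is not proven.

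The size cannot be derived from the documents. The shifts of 1 to 10 points in the working rest on 10 to 20% of true failures being read as success and no error the other way. Each is smaller than the interval's half-width, so the problem would not be visible in the results. A reader might take the coverage losses as the expected performance of the planned interval; they are illustrations under the same assumption and should not be quoted as forecasts. No number in the plan is wrong on this account. The change is worth making before data collection, but the study is not unsound without it.

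**What to change.** For the 40-minute reading, add to section 5.2.2:

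- screen the feet from the patient's view;
- test the three areas on each foot in a random order pre-printed for each patient;
- enter the patient's rating as stated, before any prompt;
- record in the eCRF whether the scorer placed the block.

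Replace the sentence in section 5.6 with a statement that scoring is unblinded, and list these measures there. Where a team member who did not place the block is available, having that person score is a useful option under section 10.2. No-contact trials are also optional. The point does not depend on either.

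The cost is a few extra minutes per patient, an order list, one eCRF field and the revised sentence, with no added staff. The time is tight. Section 5.2.2 places the block 45 minutes before surgery and the reading at 40, which leaves about 45 − 40 = 5 minutes. The sensory map and the check of effectiveness before transfer must also fit around that point, and six areas with two tests make 12 stimuli. The sequence should be tried for timing before the first patient.
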